4.4.2 Derivation rules

4.4.2.1 PARTICIPANT CLASSIFICATION FOR ADA AGAINST EFGARTIGIMOD

Table 13 below gives an overview of how the ADA participant classification will be derived, starting from the participant baseline ADA sample status. See also section 4.4.1:

Table 13: Participant classification for ADA against efgartigimod

Participant ADA classification	Highest ^c post baseline sample status				
	ADA negative	ADA positive (missing titer ^a)	ADA positive (negative titer ^b or numerical titer value)		ADA un-evaluable
Baseline ADA sample status					
ADA negative	ADA negative	Treatment-induced ADA	Treatment-induced ADA		ADA unevaluable
ADA positive (missing titer^a)	Treatment-unaffected ADA	ADA unevaluable	ADA unevaluable		ADA unevaluable
ADA positive (negative titer^b or numerical titer value)	Treatment-unaffected ADA	ADA unevaluable	titer < 4 x baseline titer: Treatment-unaffected ADA	titer ≥ 4 x baseline titer: Treatment-boosted ADA ^d	ADA unevaluable
ADA un-evaluable	ADA unevaluable	ADA unevaluable	ADA unevaluable		ADA unevaluable

^a Samples with missing titer will have a reported ADA result of 'positive immunodepletion' or 'positive titer';

^b Results reported as 'negative titer', ie, titer value <1 will be set to value of 1;

^c Highest sample status, with order: (from low to high): ADA unevaluable, ADA negative, ADA positive ('positive immunodepletion' or 'positive titer'), ADA positive with titer < 1 ('negative titer' as reported ADA result, titer value set to 1), ADA positive with titer ≥ 1 (numerical value and selecting the sample with highest titer)

^d Note: Fourfold difference in titer values is considered significant in case a twofold serial dilution is applied (= two times the dilution factor) (reference to Shankar et al., 2014)⁹

ADA evaluable participant = participant classified in any of following categories: ADA negative, treatment unaffected ADA, treatment induced ADA, treatment boosted ADA. The first two categories are classified as 'ADA negative', and the latter two are classified as 'ADA positive';

ADA unevaluable participant = participant classified as ADA unevaluable or with missing baseline ADA sample or without postbaseline ADA samples (in case no ADA data are available at all, the participant cannot be classified);

ADA incidence = percentage of participants with treatment-induced or treatment-boosted ADA (denominator: number of evaluable participants);

ADA prevalence = percentage of participants with treatment-unaffected ADA, treatment-induced ADA or treatment-boosted ADA (denominator: number of evaluable participants).

	Statistical Analysis Plan	
ARGX-113-2004	Final analysis	Final 1.0 of 7NOV2023

4.4.2.2 PARTICIPANT CLASSIFICATION FOR ANTIBODIES AGAINST rHUPH20

Table 14 below gives an overview of how the anti-rHuPH20 antibody (rHuPH20 Ab) participant classification will be derived, starting from the participant baseline rHuPH20 Ab sample status.

Table 14: Participant classification for antibodies against rHuPH20

Participant anti-rHuPH20 Ab classification	Highest ^c post baseline sample status				
	rHuPH20 Ab negative	rHuPH20 Ab positive (missing titer ^a)	rHuPH20 Ab positive ('negative titer' ^b or numerical titer value)		rHuPH20 Ab unevaluable
Baseline rHuPH20 Ab sample status					
rHuPH20 Ab negative	rHuPH20 Ab negative	Treatment-induced rHuPH20 Ab	Treatment-induced rHuPH20 Ab		rHuPH20 Ab unevaluable
rHuPH20 Ab positive (missing titer ^a)	Treatment-unaffected rHuPH20 Ab	rHuPH20 Ab unevaluable	rHuPH20 Ab unevaluable		rHuPH20 Ab unevaluable
rHuPH20 Ab positive ('negative titer' ^b or numerical titer value)	Treatment-unaffected rHuPH20 Ab	rHuPH20 Ab unevaluable	titer < 4x baseline titer: Treatment-unaffected rHuPH20 Ab	titer ≥ 4x baseline titer: Treatment-boosted rHuPH20 Ab ^d	rHuPH20 Ab unevaluable
rHuPH20 Ab unevaluable	rHuPH20 Ab unevaluable	rHuPH20 Ab unevaluable	rHuPH20 Ab unevaluable		rHuPH20 Ab unevaluable

Ab=antibody; rHuPH20= recombinant human hyaluronidase PH20

^a Samples with missing titer have as reported rHuPH20 Ab result 'positive immuno-depletion';

^b Results reported as 'negative titer', ie, titer value <5 will be set to value of 5;

^c Highest sample status, with order: (from low to high): rHuPH20 Ab unevaluable, rHuPH20 Ab negative, rHuPH20 Ab positive (missing titer/positive immuno-depletion), rHuPH20 Ab positive with titer < 5 ('negative titer' as reported rHuPH20 Ab result, titer value set to 5), rHuPH20 Ab positive with titer ≥ 5 (ie, positive titer and selecting the sample with highest titer)

^d Note: Fourfold difference in titer values is considered significant in case a twofold serial dilution is applied (reference to Shankar et al., 2014).

rHuPH20 Ab evaluable participant = participant classified in any of following categories: rHuPH20 Ab negative, treatment unaffected rHuPH20 Ab, treatment induced rHuPH20 Ab, treatment boosted rHuPH20 Ab. The first 2 categories are classified as 'rHuPH20 Ab negative', and the latter two are classified as 'rHuPH20 Ab positive'.

rHuPH20 Ab unevaluable participant = participant classified as rHuPH20 Ab unevaluable or with missing baseline rHuPH20 Ab sample or without postbaseline rHuPH20 Ab samples (in case no rHuPH20 Ab data are available at all, the participant cannot be classified);

Anti-rHuPH20 Ab incidence = percentage of participants with treatment-induced or treatment-boosted rHuPH20 Ab (denominator: number of evaluable participants)

	Statistical Analysis Plan	
ARGX-113-2004	Final analysis	Final 1.0 of 7NOV2023

Anti-rHuPH20 Ab prevalence = percentage of participants with treatment-unaaffected rHuPH20 Ab, treatment-induced rHuPH20 Ab or treatment-boosted rHuPH20 Ab (denominator: number of evaluable participants)

4.4.2.3 PARTICIPANT CLASSIFICATION FOR NAB AGAINST EFGARTIGIMOD

All ADA confirmed positive samples will also be evaluated in the NAb assay. All samples that were not analyzed in the NAb assay (ie, the ADA negative samples) are per default NAb negative. Additionally, if a NAb sample is not reported for ADA confirmed positive samples, the NAb sample status is NAb unevaluable.

All samples evaluated in the NAb assay will be scored as NAb positive, NAb negative or NAb unevaluable. Based on these results, the participants will be categorized according to their baseline and postbaseline sample status as detailed in [Table 15](#).

Table 15: Participant classification for NAb against efgartigimod

Participant NAb classification	Highest ^a post baseline NAb sample status		
	NAb negative	NAb positive	NAb unevaluable
Baseline NAb sample status			
NAb negative	baseline neg – postbaseline neg	baseline neg – postbaseline pos	NAb unevaluable
NAb positive	baseline pos – postbaseline neg	baseline pos – postbaseline pos	NAb unevaluable
NAb unevaluable	NAb unevaluable	NAb unevaluable	NAb unevaluable

NAb=neutralizing antibody; neg=negative; pos=positive

^a Highest sample status in order: (from low to high): NAb unevaluable, NAb negative, NAb positive.

NAb unevaluable participant = participant classified as NAb unevaluable or with missing baseline NAb sample or without postbaseline NAb samples (in case no NAb data are available at all, the participant cannot be classified)

NAb incidence = percentage of participant with participant classification ‘baseline neg – postbaseline pos’ and ‘baseline pos – postbaseline pos’ (denominator: number of evaluable participants)

NAb prevalence = percentage of participant with participant classification ‘baseline neg – postbaseline pos’, ‘baseline pos – postbaseline pos’ or ‘baseline pos – postbaseline neg’ (denominator: number of evaluable participants)

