Treatment	Baseline	1	-INF	1 ^b
	Week 3	22	1	36
	Week (3 + x ^c *4)	22 + (x ^c *28)	9 + (x ^c *28)	36 + (x ^c *28)
	Week 23	162	149	165
	Week 24	169	166	n ^d
Follow-up	SEFU Week 4	28	1	42
	SEFU Week 8	56	43	n ^e

^a As the interval of screening and baseline are overlapping, it may be that the same assessment will be attributed to both timepoints.

^b An assessment on day 1 will be attributed to baseline in case it is before the injection to Week 3 otherwise.

^c x ranges from 1 to 4.

^d relative day of end of treatment phase

^e relative day of end of FU phase

Baseline is defined in section 2.2.2.

Per parameter and analysis window, the value closest to the target ADY will be used in analysis tables, other values will only be listed. If more than 1 value is located at the same distance from the target, then the value latest in time will be selected. The value latest in time will be identified using, in order of preference, the assessment time, the visit label, or the group identifier. Missing values are removed before the selection is made.

For efficacy only: In case of (partially) missing date/time fields, the CRF visit label will be used to allocate to the correct analysis visit (VISIT2 becomes Week 1, VISIT3 becomes Week 2 etc.). For VISIT = END_OF_STUDY_EARLY_DISCONTINUATION the corresponding analysis visit from ADSV should be used.

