4.4.2.4 PARTICIPANT CLASSIFICATION FOR NAB AGAINST RHUPH20

All rHuPH20 Ab confirmed positive samples will also be evaluated in the NAb against rHuPH20 assay. All samples that were not analyzed in the rHuPH20 NAb assay (ie, the rHuPH20 Ab negative samples) are by default rHuPH20 NAb negative.

	Statistical Analysis Plan	
ARGX-113-2004	Final analysis	Final 1.0 of 7NOV2023

Additionally, if a rHuPH20 NAb sample is not reported, the rHuPH20 NAb sample status is rHuPH20 NAb unevaluable.

For NAb against rHuPH20, all samples evaluated in this NAb assay will be reported by the lab and scored as per [Figure 1](#). Based on these results, participants will be categorized according to their baseline and postbaseline sample status as detailed in following [Table 16](#).

Table 16: Participant classification for NAb against rHuPH20

Participant rHuPH20 NAb classification	Highest ^c post baseline sample status				
	rHuPH20 NAb negative	rHuPH20 NAb positive (missing titer ^a)	rHuPH20 NAb positive (‘negative titer’ ^b or numerical titer value)		rHuPH20 NAb un evaluable
Baseline rHuPH20 NAb sample status					
rHuPH20 NAb negative	rHuPH20 NAb negative	Treatment- induced rHuPH20 NAb	Treatment-induced rHuPH20 NAb		rHuPH20 NAb unevaluable
rHuPH20 NAb positive (missing titer^a)	Treatment- unaffected rHuPH20 NAb	rHuPH20 NAb unevaluable	rHuPH20 NAb unevaluable		rHuPH20 NAb unevaluable
rHuPH20 NAb positive (‘negative titer’^b or numeric titer value)	Treatment- unaffected rHuPH20 NAb	rHuPH20 NAb unevaluable	titer < 4x baseline titer: Treatment- unaffected rHuPH20 NAb	titer ≥ 4x baseline titer: Treatment- boosted rHuPH20 NAb	rHuPH20 NAb unevaluable
rHuPH20 NAb un evaluable	rHuPH20 NAb unevaluable	rHuPH20 NAb unevaluable	rHuPH20 NAb unevaluable		rHuPH20 NAb unevaluable

NAb=neutralizing antibody; rHuPH20= recombinant human hyaluronidase PH20

^a Samples with missing titer will be reported as having an rHuPH20 NAb result of ‘positive immunodepletion’ or ‘positive titer’;

^b Results reported as ‘negative titer’, ie, titer value <100 will be set to a value of 100;

^c Highest sample status, with order: (from low to high): rHuPH20 NAb unevaluable, rHuPH20 NAb negative, rHuPH20 NAb positive (missing titer), rHuPH20 NAb positive with titer <100 (‘negative titer’ as reported NAb result, titer value set to 100), rHuPH20 NAb positive (ie, actual titer value and selecting the sample with highest titer).

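### NAb classification lets one antibody-negative sample override an ADA-positive sample with no NAb result, so NAb incidence can be understated but never overstated

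*SAP*

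**What the plan says.** SAP 4.4.2.3 sets two rules at sample level. For samples that never reach the NAb assay: "All samples that were not analyzed in the NAb assay (ie, the ADA negative samples) are per default NAb negative". For confirmed positives that lack a result: "if a NAb sample is not reported for ADA confirmed positive samples, the NAb sample status is NAb unevaluable".

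At participant level, Table 15 crosses baseline status with the highest post-baseline status, and its footnote a fixes the order: "Highest sample status in order: (from low to high): NAb unevaluable, NAb negative, NAb positive". Incidence counts participants who are NAb positive after baseline, over this "denominator: number of evaluable participants". A participant leaves that denominator only under this definition: "NAb unevaluable participant = participant classified as NAb unevaluable or with missing baseline NAb sample or without postbaseline NAb samples".

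SAP 4.4.2.4 repeats the pattern for rHuPH20. Antibody-negative samples "are by default rHuPH20 NAb negative", and Table 16 footnote c again places unevaluable below negative. Its unevaluable rule is worded more broadly, since it is not limited to confirmed-positive samples.

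Presence of NAb is a secondary endpoint (Protocol Section 3, SAP 1.2.2) and is analysed descriptively (Protocol 9.5.10.1).

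**The concern.** For NAb, an unevaluable sample that has been confirmed ADA positive is the one sample in which neutralizing activity was an open question. An ADA-negative sample at another visit says nothing about that question. Because unevaluable ranks lowest, the uninformative sample decides the classification and a missing result is reported as a negative one.

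The SAP handles the nearest parallel the other way. In Tables 13 and 14 (SAP 4.4.2.1 and 4.4.2.2), a confirmed positive whose titer is missing ranks above negative, so negative samples at other visits do not erase it. Ranking unevaluable lowest is easier to defend in those tables, because there the antibody was never confirmed in the sample.

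The case is foreseeable. SAP 4.4.1 expects some confirmed positives to lack volume or quality for titration, and 4.4.2.3 has a rule for NAb results that are not reported.

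The efgartigimod NAb class drives incidence and prevalence (Table 14.2.11.2), NAb by ADA class (14.2.11.3), and the platelet, PK, IgG and adverse-event tables by NAb class (the 14.2.12 series). The rHuPH20 NAb class does not feed those correlation tables, which use the rHuPH20 binding-antibody class instead.

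**Working it through.** The plan states no NAb rate, so there is no figure to reproduce. The check applies the rules to sample patterns and then illustrates the size.

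**Windows.** SAP 2.2.4, Table 7, has weeks 3, 23 and 24, plus weeks 3 + 4x where "x ranges from 1 to 4", giving weeks 7, 11, 15 and 19. That is 3 + 4 = 7 post-baseline windows in the treatment phase, so an ADA-negative neighbour is easy to find.

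**Enumeration under Table 15** (ADA+? = ADA confirmed positive with no NAb result; ADA- = ADA negative):

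| Baseline | Post-baseline samples | Classification | In denominator | In incidence |
|---|---|---|---|---|
| NAb negative | 1 ADA+?, 6 ADA- | baseline negative, post-baseline negative | yes | no |
| NAb negative | 6 ADA+?, 1 ADA- | baseline negative, post-baseline negative | yes | no |
| NAb negative | 7 ADA+? | unevaluable | no | no |
| NAb negative | one sample only, ADA+? | unevaluable | no | no |
| ADA+? | 7 ADA- | unevaluable | no | no |
| NAb positive | 1 ADA+?, 6 ADA- | baseline positive, post-baseline negative | yes | no (counts in prevalence) |

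Rows 1 and 2 are the problem. Even six unresolved positives are overridden by one ADA-negative sample.

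**Direction.** Let n be evaluable participants, x those detected as NAb positive after baseline, k the participants in rows 1-2, and t (between 0 and k) those of the k who are truly NAb positive. The SAP reports x/n. The true rate is (x + t)/n. Since t cannot be negative, x/n is at or below the true rate, with equality when t = 0. Calling the k participants unevaluable gives x/(n - k).

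**Illustration.** Planned numbers (SAP 1.4) are 180 + 39 = 219 randomized 2:1, so 219 x 2/3 = 146 on efgartigimod. I take all 146 as evaluable. The values of x and k are assumptions.

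| x | k | SAP rule x/n | k unevaluable x/(n - k) | all k truly positive (x + k)/n |
|---|---|---|---|---|
| 5 | 1 | 3.42% | 3.45% | 4.11% |
| 5 | 3 | 3.42% | 3.50% | 5.48% |
| 5 | 5 | 3.42% | 3.55% | 6.85% |
| 2 | 5 | 1.37% | 1.42% | 4.79% |
| 10 | 5 | 6.85% | 7.09% | 10.27% |

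With k = 0 all three columns agree.

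**Expected shortfall.** Assume 10-30% of the 146 are ADA confirmed positive at some visit (15-44 participants) and 5-10% of those are affected. That is 0.05 x 14.6 = 0.7 to 0.10 x 43.8 = 4.4, or about 1-4 participants. If missingness is unrelated to NAb status, the expected share of true NAb positives missed equals the share affected, 5-10%. With true NAb incidence of 2-5% (3-7 participants), that is 0.05 x 3 = 0.15 to 0.10 x 7 = 0.7 participants.

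**The case against.** Ranking unevaluable lowest is the SAP's uniform convention in Tables 13 to 16. SAP 4.4.2.3 plans NAb testing of every ADA confirmed positive, so there may be no affected participant at all. Unresolved samples are not hidden: NAb status is tabulated by visit (Tables 14.2.11.1 and 14.2.11.4) and listed beside the participant class (Listings 16.2.6.8 and 16.2.6.9). NAb lies outside the testing hierarchy in SAP 4.1.3.1. All of this stands and limits the importance of the point. None of it changes the participant-level classification, and no rule or sensitivity analysis in the SAP corrects it.

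The objection is also right about the obvious repair. Simply moving unevaluable above negative would make a baseline-NAb-positive participant (last row of the enumeration) unevaluable, removing a known positive from prevalence. It would also discard participants whose other ADA-positive samples were tested and found NAb negative.

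A reader might infer that unevaluable arises only when every post-baseline sample is unresolved. Table 15 and the accompanying definition do not support that: an unevaluable or missing baseline, or no post-baseline sample, gives the same result.

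**Conclusion.** The point holds as a conditional one. It applies to a participant with a NAb-negative baseline, at least one post-baseline confirmed-positive sample, no NAb result on any such sample, and at least one other post-baseline sample that is antibody negative. That participant is counted as negative, and the error in incidence can go only downward.

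A reader might go further and say that incidence is understated, or that a large part of the NAb signal is lost because one missed case among 3-7 true positives is 14-33% (1/7 to 1/3). The documents support neither. They give no rate of missing NAb results, and the second reading presumes that an affected participant is truly NAb positive. On the stated assumptions the expected relative shortfall is about 5-10%, less than one participant.

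This is a small effect on a descriptive secondary endpoint. It is worth correcting because the direction is fixed, the SAP's own ADA tables avoid the equivalent step, and the change is cheap.

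**What to change.** In Tables 15 and 16, add one rule. A baseline-NAb-negative participant with at least one post-baseline ADA (or rHuPH20 antibody) confirmed-positive sample is NAb unevaluable when no post-baseline sample is NAb positive and none of those confirmed-positive samples has a NAb result. Keep the default-negative rule for antibody-negative samples. Leave baseline-NAb-positive participants as now classified, so that they stay in prevalence. Report the number of participants affected beside NAb incidence.

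The cost is two footnotes, one programmed condition and one count. The evaluable denominator falls slightly, and incidence could be slightly overstated if the excluded participants are truly negative: with x = 5 and k = 5, 3.55% against 3.42%. The rule does not recover missed positives, since the numerator is unchanged. It stops missing results being reported as negative, and the count lets the reader bound the rate.

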4.4.2.4 PARTICIPANT CLASSIFICATION FOR NAB AGAINST RHUPH20

All rHuPH20 Ab confirmed positive samples will also be evaluated in the NAb against rHuPH20 assay. All samples that were not analyzed in the rHuPH20 NAb assay (ie, the rHuPH20 Ab negative samples) are by default rHuPH20 NAb negative.

	Statistical Analysis Plan	
ARGX-113-2004	Final analysis	Final 1.0 of 7NOV2023

Additionally, if a rHuPH20 NAb sample is not reported, the rHuPH20 NAb sample status is rHuPH20 NAb unevaluable.

For NAb against rHuPH20, all samples evaluated in this NAb assay will be reported by the lab and scored as per [Figure 1](#). Based on these results, participants will be categorized according to their baseline and postbaseline sample status as detailed in following [Table 16](#).

Table 16: Participant classification for NAb against rHuPH20

Participant rHuPH20 NAb classification	Highest ^c post baseline sample status				
	rHuPH20 NAb negative	rHuPH20 NAb positive (missing titer ^a)	rHuPH20 NAb positive (‘negative titer’ ^b or numerical titer value)		rHuPH20 NAb un evaluable
Baseline rHuPH20 NAb sample status					
rHuPH20 NAb negative	rHuPH20 NAb negative	Treatment- induced rHuPH20 NAb	Treatment-induced rHuPH20 NAb		rHuPH20 NAb unevaluable
rHuPH20 NAb positive (missing titer^a)	Treatment- unaffected rHuPH20 NAb	rHuPH20 NAb unevaluable	rHuPH20 NAb unevaluable		rHuPH20 NAb unevaluable
rHuPH20 NAb positive (‘negative titer’^b or numeric titer value)	Treatment- unaffected rHuPH20 NAb	rHuPH20 NAb unevaluable	titer < 4x baseline titer: Treatment- unaffected rHuPH20 NAb	titer ≥ 4x baseline titer: Treatment- boosted rHuPH20 NAb	rHuPH20 NAb unevaluable
rHuPH20 NAb un evaluable	rHuPH20 NAb unevaluable	rHuPH20 NAb unevaluable	rHuPH20 NAb unevaluable		rHuPH20 NAb unevaluable

NAb=neutralizing antibody; rHuPH20= recombinant human hyaluronidase PH20

^a Samples with missing titer will be reported as having an rHuPH20 NAb result of ‘positive immunodepletion’ or ‘positive titer’;

^b Results reported as ‘negative titer’, ie, titer value <100 will be set to a value of 100;

^c Highest sample status, with order: (from low to high): rHuPH20 NAb unevaluable, rHuPH20 NAb negative, rHuPH20 NAb positive (missing titer), rHuPH20 NAb positive with titer <100 (‘negative titer’ as reported NAb result, titer value set to 100), rHuPH20 NAb positive (ie, actual titer value and selecting the sample with highest titer).

rHuPH20 NAb evaluable participant = participant classified in any of following categories: rHuPH20 NAb negative, treatment unaffected rHuPH20 NAb, treatment induced rHuPH20 NAb, treatment boosted rHuPH20 NAb. The first 2 categories are classified as ‘rHuPH20 NAb negative’, and the latter two as ‘rHuPH20 NAb positive’;

rHuPH20 NAb unevaluable participant = participant classified as rHuPH20 NAb unevaluable or with missing baseline rHuPH20 NAb sample or without postbaseline rHuPH20 NAb samples (in case no rHuPH20 NAb data are available at all, the participant cannot be classified);

	Statistical Analysis Plan	
ARGX-113-2004	Final analysis	Final 1.0 of 7NOV2023

Anti-rHuPH20 NAb incidence = percentage of participant with treatment-induced or treatment-boosted rHuPH20 NAb (denominator: number of evaluable participants);

Anti-rHuPH20 NAb prevalence = percentage of participant with treatment-unaffected rHuPH20 NAb, treatment-induced rHuPH20 NAb or treatment-boosted rHuPH20 NAb (denominator: number of evaluable participants).

4.4.3 *Presentation of results*

Analysis will be performed for ADA against efgartigimod and antibodies against rHuPH20.

Frequency tabulations (number and percentages) will be provided with ADA or rHuPH20 Ab negative/positive/unevaluable samples per visit. This will be repeated for following subgroups: receiving concurrent ITP therapies at baseline, and type of concurrent ITP therapies at baseline.

Frequency tabulations (number and percentages) for efgartigimod and rHuPH20 will be provided on:

- participants per ADA or rHuPH20 Ab participants classification
- prevalence and incidence of ADA or rHuPH20 Ab
- ADA or rHuPH20 Ab unevaluable participants
- ADA or rHuPH20 Ab baseline positive/negative/unevaluable samples

For details on the definitions, see the above section [4.4.2.1](#) and [4.4.2.2](#).

The above frequency tabulations will be repeated for NAb assay using the definitions as defined in section [4.4.2.3](#) and [4.4.2.4](#).

In addition, a frequency tabulation (number and percentages) will be provided for:

- Nab against efgartigimod positive participants within efgartigimod ADA participants classification (Treatment-unaffected ADA, Treatment-induced ADA, Treatment-boosted ADA, ADA negative and ADA unevaluable).
- NAb against rHuPH20 Ab positive participants within rHuPH20 Ab participants classification.
- rHuPH20 Ab positive participants within efgartigimod ADA participants classification.

Correlation tables by ADA and NAb participant classification against efgartigimod and by antibodies participant classification against rHuPH20 will be provided for the following parameters:

- Mean drug concentration over time
- Mean percent change from baseline in platelet count
- Mean percent change from baseline in total IgG
- Number and percentage of sustained platelet count response (key secondary endpoint (week 19 – 24) in the overall population)
- Overall Treatment-Emergent Adverse Events by MedDRA System Organ Class and Preferred Term by Overall Anti-Drug Antibodies Participant Classification (All Participants)

	Statistical Analysis Plan	
ARGX-113-2004	Final analysis	Final 1.0 of 7NOV2023

- Overall Serious Treatment-Emergent Adverse Events by MedDRA System Organ Class and Preferred Term by Overall Anti-Drug Antibodies Participant Classification (All Participants)
- Overall injection-related reactions (IRR) by Overall Anti-Drug Antibodies Participant Classification (All Participants)
- Overall injection site reactions (ISR) by Overall Anti-Drug Antibodies Participant Classification (All Participants)

Correlation tables on mean drug concentration over time, on mean percent change from baseline in platelet count, on mean percent change from baseline in total IgG and on number and percentage of sustained platelet count response can be restricted to the efgartigimod treated participants only. The other correlation tables must be provided for efgartigimod and placebo treated participants.

ADA titer values against efgartigimod and rHuPH20 Ab titer values will be summarized by means of descriptive statistics by ADA participant classification or rHuPH20 Ab participant classification respectively.

All available data on ADA and NAb against efgartigimod, and rHuPH20 Ab and rHuPH20 NAb will be listed, showing also the ADA and NAb sample status and participant classification.

	Statistical Analysis Plan	
ARGX-113-2004	Final analysis	Final 1.0 of 7NOV2023

